7. ADVERSE EVENTS AND REPORTING PROCEDURES

References for SCI adverse event (AE) policies and practices are provided in Appendix A.

7.1. Adverse Event Definitions

An adverse event is any untoward medical occurrence associated with the use of a drug in humans, whether or not considered drug-related. An adverse event can be any unfavorable and unintended sign or symptom, including abnormal laboratory findings, or disease, that is temporally associated with the use of a drug, and does not imply any judgment about causality. An adverse reaction is any event that is caused by a drug or device, ie, possibly-, probably-, or definitely-related to the use of the drug or device.

Except as otherwise explicitly defined within this section, **this also includes all events of clinical deterioration such as tumor relapse, recurrence, or upstaging, or new cancers.**

Within the scope of this study and protocol, adverse device effects, ie, events that have a serious adverse effect on health or safety or any life-threatening problem or death caused by, or associated with, a device may be referred to as “serious adverse events (SAEs).”

Serious adverse events (SAEs) are defined per the FDA definition at 21CFR§312.32(a) and ICH GCP E6. An adverse event is considered "serious" if, in the opinion of the PD, investigator, or sponsor, it results in ANY of the following.

- Death
- Life-threatening adverse event with an **actual and immediate risk of death** [21CFR§312.32(a)]
- Inpatient hospitalization or prolongation of existing hospitalization, except planned hospitalization or hospitalization only for study conduct will not be considered SAEs
- A persistent or significant incapacity or substantial disruption of the ability to conduct normal life functions
- A congenital anomaly/birth defect
- Event jeopardizes the subject and may require medical or surgical intervention to prevent one of the outcomes listed here

7.2. Classification of Adverse Events

7.2.1. Severity of Event

NCI CTCAE version 5.0 is used to assess the severity of adverse events in this study.

7.2.2. Adverse Event Attribution to Intervention or Study

For this study, all recorded adverse events will be assessed on the basis of whether or not the adverse event was caused by / due to (ie, related) to the study intervention(s). AEs, serious or otherwise, will be attributed by the Principal Investigator or qualified designate to study treatment in accordance with the definitions below.

7.2.4. Time Period of Event Assessment and Follow-up

Once the participant signs the consent form, any adverse event that occurs during their study period (approx.. 6-weeks) will be kept track of once the study team learns of the event.

All possibly study related SAEs will be followed until resolution.

7.3. Potential Adverse Events and Risks

Potential adverse events and risks were described at Section 1.3.1 Known Potential Risks.

In addition to the summary risks described in Section 1.3.1, adverse events described by severity and frequency within the informed consent are considered anticipated, ie, not unexpected. Procedural risks described in Section 1.3.1 are considered anticipated.

7.4. Adverse Event Monitoring and Collection

Untoward medical events experienced by a study subject during the study intervention period (6-weeks) will be considered an adverse event (AE), regardless of whether or not considered intervention-related. All events of disease progression or second cancer will be recorded as a serious adverse event (SAE) using the Preferred Term appropriate for the clinical finding.

7.4.1. Case Report Forms for Adverse Event Reporting

Both SAEs and non-serious adverse events will be described in source documentation and listed on study-specific Case Report Forms (CRFs or eCRFs).

Adverse events will be recorded on a log (see references in Appendix A) providing the unique subject identifier, event preferred term, CTCAE body system, date of occurrence, date of resolution; and type of resolution. All signs, symptoms, significant laboratory findings, AND diagnoses should be recorded, regardless of relationship, except as described in this document. A single “overarching” diagnosis should not be solely entered as the adverse event term in lieu of the full list of observed signs, symptoms, and significant laboratory findings, which may include the diagnostic preferred term.

Types of resolution are:

- “Resolved,” ie, to Grade 0 (or baseline if a pre-existing condition)
- “Continuing” and stable (includes downgrades from a higher grade to a lower grade)
- “Deceased” (due to any cause while on-study)
- Lost-to-follow-up.
- **NOTE:** “Hospitalized” is not an outcome.

Any pre-existing condition that worsens in severity or frequency should be recorded as a new adverse event, except as described in this document.

7.5. Adverse Events of Special Consideration

7.5.1. Second vs Secondary Malignancy

7.5.1.1. Second Malignancy

A second malignancy is one unrelated to the treatment of a prior malignancy (and is NOT a metastasis from the initial malignancy). A second malignancy is by definition a serious adverse event (SAE), and will be recorded and reported accordingly.

7.5.1.2. Secondary Malignancy

In the context of a clinical study, a secondary malignancy is a cancer caused by chemotherapy, radiation, or the investigational agent/intervention. A secondary malignancy is not considered a metastasis of the initial neoplasm, but nonetheless, a secondary malignancy is by definition a serious adverse event (SAE), and will be recorded and reported accordingly. Secondary malignancies are usually described as one of the following:

- Leukemia secondary to oncology chemotherapy [eg, acute myelocytic leukemia (AML)]
- Myelodysplastic syndrome (MDS)
- Treatment-related secondary malignancy

By definition, secondary malignancies are adverse events that are both serious and related to the research, and should be anticipated to be an Unanticipated Problem (UP) and reported accordingly. If also determined to be related to the study treatment, and not described by the Investigator Brochure or package insert as known to be associated with the study agent, the secondary malignancies may also necessitate Expedited Reporting to FDA, eg, an IND Safety Report to the IND.

7.5.2. Progressive Disease

Progressive disease will be reported by the clinical signs or symptoms of disease progression. If the event is Grade 5 fatal and signs/symptoms of disease progression are not available / informative for the event, the CTCAE v5.0 preferred term “Disease Progress” may be used.

7.5.3. Other Adverse Events of Special Considerations

None.

7.6. Adverse Event Reporting

Reportable adverse events, based on relatedness (attribution) to the study agent; expectedness, severity (Grade 1 to 5), seriousness (Yes/No), or any other aspect of the investigation, will be reported as described below.

- Whenever possible, diagnoses should be given when signs and symptoms are due to a common etiology (eg, cough, runny nose, sneezing, sore throat; and head congestion should be reported as "upper respiratory infection").

- Serious adverse events (SAEs) per the definition at [21CFR§312.32](#) will be reported to the investigator **within 24 hours of the knowledge of the event**. Possibly study related SAEs will be reported to the MindCotline.
- SAEs will be reported to the SCI Data and Safety Monitoring Committee (DSMC) by submission to CCTO-Safety. The event must be described on either the SCI SAE form (see references in Appendix A), or a study-specific form. If applicable, the Form FDA 3500A (see Section 7.6) for mandatory IND Safety Reports may be substituted. The report will be sent by **secure** email to [contact] at the time of the **first** notification to MindCotline (if possibly study related); or the IRB of record. The SAE form must be signed by the investigator. CCTO-Safety will process the SAE report into OnCore, and the DSMC will review the event. See the SCI Data Safety and Monitoring Plan (DSMP).
- **All Unanticipated Problem (UPs)** associated with the use of a drug, biologic, or device will be reported as follows.
 - Note that for the purposes of Stanford IRB Unanticipated Problem reporting, subjects are considered to be study participants when consented, ie, events during screening and/or pre-treatment through that subject's official end of study participation may qualify as reportable.
 - To the Stanford IRB, by the Stanford Protocol Director, if an adverse event meets the Stanford IRB's current definition of an Unanticipated Problem (UP) as specified by the IRB document "Events and Information that Require Prompt Reporting to the IRB" (GUI-P13), per the timeframes defined therein. See also Section 9.4 Data and Safety Monitoring Plan. In addition to event triggered expedited UP reports, all UPs should be summarized in the Continuing Review, with, as applicable, a discussion of any change in assessment of risk (ie, different than previously described).
 - To the SCI Data and Safety Monitoring Committee (DSMC), by submission to CCTO-Safety / OnCore as an SAE (see SAE reporting to DSMC above. See also the SCI DSMP).

Serious adverse events (SAEs) will be reported to the IRB of record and to the DSMC in accordance with the applicable guidelines and regulations.

Serious adverse events (SAEs) will be reported to the IRB of record in accordance with the applicable guidelines, regulations, and SOPs (see references in Appendix A).

7.7. Adverse Event Records

The investigator will retain adverse event source data, supporting documentation of attribution and seriousness, and copies of official adverse event reports or SAE CRFs, as well as documentation of informal communications (such as telephone calls or emails) in accordance with the current version of Stanford School of Medicine standard operating procedure SOP-005 "Identifying and Reporting Adverse Events" (see references in Appendix A).

7.8. Risk Mitigation

[name] will be informed of all SAEs that occur during the study within 24 hours upon learning of the event, and the participant will be follow up with as appropriate.

8. CORRELATIVE / SPECIAL STUDIES

None

8.1. Correlative Studies Background

None

8.2. Laboratory Correlative Studies

None.

9. REGULATORY CONSIDERATIONS AND DATA REPORTING

9.1. Review and Approval of Protocol by IRB and SCI SRC

This protocol, the proposed informed consent, and all forms of information related to the study that will be provided to the subjects (eg, questionnaires, handouts, written instructions, diaries, advertisements used to recruit subjects, etc) will be submitted to, reviewed, and approved by the SCI Scientific Review Committee (SRC) and the Stanford Administrative Panels on Human Subjects in Medical Research of the Research Compliance Office (ie, the Stanford IRB)”) prior to initiation of the research. Any changes made to the protocol will be submitted as a modification and will be approved by the IRB of record prior to implementation.

This study will be conducted in accordance with the iteration of the protocol that is currently IRB-approved.

9.2. Protocol Compliance and Deviations

9.2.1. Compliance with the Protocol

No deviation or changes from the procedures and process described by the IRB-approved protocol, except those necessary to eliminate an immediate hazard(s) to trial subjects, or when the change(s) involves only logistical or administrative aspects of the trial [eg, change in study monitor(s), change of telephone number(s)], will be knowingly permitted without review and approval by the IRB of record.

9.2.2. Protocol Deviations

Any deviation (or violation) from the IRB-approved protocol, including those that eliminate an immediate hazard or are administrative in nature, will be documented and explained in the study

site file. All deviations at the Stanford clinical that meet the reporting requirements defined in the Stanford University HRPP Policy Guidance “Events and Information that Require Prompt Reporting to the IRB” GUI-P13 will be reported to the Stanford IRB by the Stanford investigator within the defined timeframes. All deviations will be reported to the Stanford IRB either annually in the IRB continuing review, or individually as IRB Prompt Reports (within 5 or 10 working days, see GUI-P13).

For all studies monitored by the SCI Data and Safety Monitoring Committee (DSMC) as defined in Section 9.3 Data and Safety Monitoring Plan, all deviations, exceptions, and/or violations of the protocol, as well as deviations, exceptions, and/or violations to applicable IRB policies and overarching regulations, will be reported to the SCI data Safety and Monitoring Committee (DSMC). Accordingly, as the DSMC only reviews reports recorded in OnCore, such events will be promptly submitted in the OnCore record for the study, per the current SCI DSMC SOP.

9.3. Data and Safety Monitoring Plan

The Principal Investigator is responsible for monitoring the conduct of the study including oversight of safety and protocol compliance. On an ongoing basis, the Principal Investigator will review safety data and identify any changes to the research necessary to ensure the appropriate measures and monitoring necessary for participant safety. In addition to the Principal Investigator’s safety monitoring role, the SCI DSMC will conduct data and safety monitoring activities for this study.

9.3.1. Monitoring

The Principal Investigator will be the monitoring entity for this study. The study data safety monitoring plan (DSMP) must be commensurate with the risk of the study design with adequate measures for oversight of data and safety monitoring. The Principal Investigator will audit study-related activities to determine whether the study has been conducted in accordance with the protocol, local standard operating procedures, FDA regulations, and GCP. This may include review of the following types of documents participating in the study: regulatory binders, case report forms, eligibility checklists, and source documents. In addition, the Principal Investigator will regularly review serious adverse events and protocol deviations associated with the research to ensure the protection of human subjects. Results of the Principal Investigator’s monitoring efforts will be communicated to the respective IRB of record and appropriate regulatory authorities at the time of continuing review, or in an expedited fashion, as needed.

9.3.1.1. Investigator Monitoring

Pursuant to the Guideline for GCP, monitoring is defined as the act of overseeing the progress of a clinical trial, and of ensuring that it is conducted, recorded, and reported in accordance with the protocol, standard operating procedures (SOPs), GCP, and the applicable regulatory requirement(s).

The Principal Investigator is responsible for self-monitoring the progress of the trial on a continuous basis. Self-monitoring includes, but is not limited to, those items that will be reviewed during an audit (see also Section 9.5).

9.4. Data Management

Source documents for all research data will be retained in accordance with all applicable regulations and institutional requirements for data retention. These materials will be made available for monitoring and/or auditing by SCI DSMC, other monitoring body and/or regulatory agencies.

9.4.1. Data Management Plan

The study data will be collected via the **REDCap or Qualtrics** central online database, with password-protected access limited to the study team .

The Stanford Principal Investigator will provide a data monitoring plan describing how and when the Stanford Principal Investigator and/or designates will monitor the study. The monitoring will be adequate to assure that the valid consent is obtained and documented; the per-protocol data are collected; records and databases are maintained with adequate and accurate participant case histories; adverse events are reported; clinical protocol is maintained; and the study is conducted according to the established procedures of the IRB of record. Original source documents include clinical charts and hospital, laboratory, and pharmacy records.

9.5. Site Documentation and Management

The following information will be maintained by the Principal Investigator at the participating site.

- Delegation of Authority Log, indicating study role, training date, on-study date (date of first research-related procedure or scan), and off-study date
- Financial Disclosure Forms and updates
- Copies of all correspondence with the IRB of record, including all approval letters and approved template informed consent documents, in chronological order by date.
- Copies of all correspondence with the local Scientific Review Committee, including approval letters, renewals, and other types of communication.
- Study agent accountability log
- Serious adverse event (SAE) log, documenting the subject, date, event, relatedness, follow-up, and outcome, with dates of communication to the IRB of record and Oncore/CCTO-Safety (Stanford site).
- Log of Deviations (ie, excursions from the protocol not authorized by the Stanford investigator and approved by the IRB). The Log of Deviations must be maintained in OnCore.
- Laboratory documentation, including copies of local site CAP and CLIA certificates, State licenses, laboratory director CV and medical license, with laboratory normal values/reference ranges for all labs used in the study.
- Printed, dated copy of roster for IRB of record, for each year of the study.

9.6. FDA Oversight

9.6.1. Investigational New Drug (IND) Application Considerations N/A

9.6.2. Investigational Device Exemption (IDE) Application Considerations

Exempted Device Investigation

This study describes the use of a device in a study that is considered to not require an Investigational Device Exemption (IDE), as elucidated at 21CFR§812.2(c). This study will be submitted to the IRB of record, and their approval obtained, before the study is initiated.

10. STATISTICAL CONSIDERATIONS

A pilot study (n=20), with short-term outcomes, and limited data collection, the statistical plan is descriptive in nature. Feasibility metrics would be at least (i) 20% interested in using the app; (ii) 75% of interested patients onboarded and using the app; and (iii) 70% recommending the app to others. Efficacy goals will be examining tobacco use reduction and quitting with goals of at least (iv) 50% reducing tobacco use and 10% quitting. Descriptive statistics (e.g., means/SD, frequencies, ranges) will summarize participant demographic and tobacco use characteristics, changes in tobacco use over time, MindCotine app usage, feedback on the MindCotine program, dropout and any adverse effects. The quit rate among participants in this pilot will be compared to the quit rate for our tobacco treatment service as a clinical benchmark.

10.1. Statistical Plan

A pilot study (n=20), with short-term outcomes, and limited data collection, the statistical plan is descriptive in nature.

10.1.1. Method of Treatment Assignment

All 20 participants will receive the VR kit with an activation code to access the full MindCotine program.

10.1.2. Sample Size Determination

This is a pilot study to see if MindCotine is feasible for patients from the Stanford Cancer Center who smoke. MindCotine will be providing 20 VR kits for free for this purpose. The sample size is N=20. We view a sample size of 20 as sufficient to gain an initial understanding of interest in the program and use of the program in our patient population.

10.1.3. Minimization of Bias

App usage is collected from the MindCotine app – it is not self-reported. Assessment items collecting feedback on MindCotine are non-leading. Standard measures of participant characteristics and tobacco use are utilized.

10.2. Study Endpoints

Feasibility metrics would be at least (i) 20% interested in using the app; (ii) 75% of interested patients onboarded and using the app; and (iii) 70% recommending the app to others. Efficacy goals will be examining tobacco use reduction and quitting with goals of at least (iv) 50% reducing tobacco use and 10% quitting.

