2. STUDY DESIGN, OBJECTIVES, AND OUTCOMES

2.1. Study Design

2.1.1. Overall Design

The intervention model of this study is **Single Group**.

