2.1.3. Study Cohorts / Arms / Groups

Pre/post-intervention design. Participants' tobacco use will be compared at two timepoints: Enrollment, and End of treatment.

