2.1.4. Scientific Justification for Study Design

This study is a pilot to test feasibility of the app among patients from the Stanford Cancer Center who smoke cigarettes daily. There will be 20 kits available for testing feasibility. Outcomes will be assessed pre-intervention and post-intervention.

Factors that indicate feasibility will include (i) interest among our patient population in using the app, which will be offered at no cost; (ii) among those patients who are interested, that they are able to onboard and make use of the app; and (iii) patient ratings of recommending the app to others. Feasibility metrics would be at least (i) 20% interested in using the app; (ii) 75% of interested patients onboarded and using the app; and (iii) 70% recommending the app to others. Efficacy goals will be examining tobacco use reduction and quitting with goals of at least (iv) 50% reducing tobacco use and 10% quitting. Not feasible would be indicated by **less than** (i) 20% interested in using the app; (ii) 75% of interested patients onboarded and using the app; and (iii) 70% recommending the app to others.

Given the novelty of the program (virtual reality app) and our older patient population, we are interested in seeing do patients have interest in using the program, are they able to onboard at a distance (from home), do they make use of the app, and would they recommend the app to others. We also will examine whether they reduce or quit their tobacco use. If the metrics above are met, we would consider adding MindCotine to the choices available.

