10.2.2. Secondary Endpoint(s)

Quitting, making a quit attempt during the past 6 weeks, use of cessation medications, smoking reduction (ie., change in cigarettes per day from baseline), MindCotine usage, MindCotine dropout, and adverse events.

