10.5.1. Secondary Analysis Population

Full sample N=20.

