10.5.2. Secondary Analysis Plan

Frequency calculation of quit attempts, use of cessation medications, MindCotine dropout, and adverse events. We will calculate the mean change in reported cigarettes per day from baseline to EOT. We will calculate mean scores for MindCotine app usage.

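### The reduction half of efficacy goal (iv) sets no minimum drop in a single-group pre/post design, so random fluctuation alone can meet it

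*Combined protocol and SAP*

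**What the plan says.** Section 10.2 sets the goal: "Efficacy goals will be examining tobacco use reduction and quitting with goals of at least (iv) 50% reducing tobacco use and 10% quitting". The same goal appears in the synopsis and in sections 2.1.4 and 10. The parallel 10% for quitting shows that the 50% is a share of participants, not a 50% cut in consumption.

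Section 10.2.2 describes the measure only as "smoking reduction (ie., change in cigarettes per day from baseline"), with no responder cut-off. Section 10.5.2 plans a mean: "We will calculate the mean change in reported cigarettes per day from baseline to EOT". The proportion that the goal refers to is not listed in section 10.5 or 10.5.2.

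On design, section 2.1.1 says "The intervention model of this study is Single Group", and section 2.1.3 says "Participants' tobacco use will be compared at two timepoints: Enrollment, and End of treatment". Section 1.3.2 allows other cessation treatment alongside the app. The external benchmark in section 10 covers the quit rate, not reduction. Section 10.5 treats dropouts as still using tobacco when quitting is counted, but gives no dropout rule for reduction.

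On use of the result, section 2.1.4 lists the feasibility metrics and the efficacy goals and then says "If the metrics above are met, we would consider adding MindCotine to the choices available".

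**The concern.** Taken literally, one cigarette a day fewer makes a participant a reducer. Self-reported smoking varies from week to week. If the app does nothing and reports fluctuate symmetrically around a stable level, a participant is as likely to report less as to report more. The share reporting less is then half of those who do not tie, which is at most 50%. The target of 50% therefore sits at the upper end of what no effect would produce, and in 20 people chance can readily reach it.

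At stake is how the team reads the result. Meeting the reduction half could be taken as support for offering the app when it may be noise. Adding the missing proportion to section 10.5 would not cure this: a correctly calculated proportion with no minimum drop has the same weakness.

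**Working it through.** **Inputs from the documents.** N = 20, fixed by supply (section 10.1.2: "MindCotine will be providing 20 VR kits for free for this purpose. The sample size is N=20"). Section 10.5.1 gives the population: "Full sample N=20". The sample size has no formula behind it, so there is no stated operating characteristic to reproduce. The thresholds are 0.50 × 20 = 10 reducers and 0.10 × 20 = 2 quitters.

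**Assumed inputs.** The share of tied reports, within-person variability, drift, dropout and background quit rate are not in the documents and are shown as ranges.

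**1. No app effect, symmetric fluctuation, no dropout.** The chance that one participant reports less is p = (1 − tie share)/2. The chance that the reduction half is met is P(X ≥ 10) for X ~ Binomial(20, p).

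| Tie share | p | P(≥10 of 20) |
|---|---|---|
| 0% | 0.50 | 0.588 |
| 10% | 0.45 | 0.409 |
| 20% | 0.40 | 0.245 |
| 30% | 0.35 | 0.122 |
| 40% | 0.30 | 0.048 |

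**2. On the plan's measure, cigarettes per day.** Rounding creates ties. A simulation with no true change assumed a median of 50–100 cigarettes per week, log-SD 0.7 between people, a week-to-week coefficient of variation of 15–35%, and entry above 9 cigarettes per week. On rounded cigarettes per day the goal is met about 14–46% of the time with no dropout, and about 3–16% with 20% dropout counted as non-reducers. On unrounded 7-day counts, where ties are few, the figures are 51–57% and 20–23%.

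**3. Dropout handling.** With 4 of 20 missing and no ties, P = 0.227 if the missing count as non-reducers out of 20, and 0.598 if only the 16 completers are counted (8 needed). The plan does not say which applies to reduction.

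**4. Drift without an app effect.** Motivation at entry, other treatment or reporting tendencies could raise p. At p = 0.55, P = 0.751; at p = 0.60, P = 0.873.

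**5. Both halves of (iv).** Section 1.2.3 reports 5% abstinence in the control group of the earlier app trial; I use 5% as an assumed background quit rate. P(at least 2 quitters of 20) = 1 − 0.95^20 − 20 × 0.05 × 0.95^19 = 1 − 0.358 − 0.377 = 0.264. Counting quitters as reducers, and letting each non-quitter reduce with chance p, the joint chance is Σ (x ≥ 2) P(x quitters) × P(Binomial(20 − x, p) ≥ 10 − x). This gives about 0.13 at p = 0.40 and 0.21 at p = 0.50, with no dropout.

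**6. Effect of a minimum drop.** Let s be the within-person SD of log consumption at each time, assumed to be 0.2–0.5. The chance of a drop of at least a fraction c is Φ(ln(1 − c)/(s√2)).

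- c = 0.25: 0.15 to 0.34 per person; P(≥10 of 20) is 0.0003 to 0.107.
- c = 0.50: 0.007 to 0.16 per person; P(≥10 of 20) is at most 0.0005.

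**The case against.** The strongest reply has four parts.

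- **The goal has two halves.** A reader might infer that goal (iv) cannot tell an effective app from an inert one. The documents do not support that, because the same item also asks for 10% quitting. If nobody would quit without the app, fluctuation would almost never meet the whole goal; at 5% background quitting the chance is capped at 26%. This stands, and it limits the point to the reduction half.
- **The highest figures are not on the plan's measure.** The 59% needs no ties and no dropout, and the 51–57% needs 7-day counts. The plan specifies cigarettes per day, where the range is lower. This stands. It is also tempting to say that enrolling people who have just agreed to treatment, and letting them use other services, can only push the chance rate up. Those factors may raise it, but ties and dropout pull it down.
- **The goal carries limited weight.** The primary endpoint is feasibility and acceptability (section 10.2.1), the not-feasible rule in section 2.1.4 lists only (i) to (iii), the plan is descriptive (section 10.1), and efficacy is left to a larger powered study (sections 10.5.4.2 and 10.5.4.3). Mean change is also reported, so a trivial average reduction would be visible. All this limits the severity. It does not remove the problem, because a goal stated in advance should mean something when it is met.
- **A cut-off is a choice and not a full cure.** No section supports halving in particular, and a cut-off does not deal with drift or other treatment. The end-of-treatment cigarette question is not visible in the available text, so a matching 7-day window cannot be confirmed. These points stand and shape the fix.

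**Conclusion.** The point holds for the reduction half of goal (iv). As written, chance alone meets it about 14–46% of the time on rounded cigarettes per day with no dropout, and up to 59% without ties. At 20% dropout counted as non-reducers, the range is about 3–23% across both ways of counting. With both halves required, the chance is about 13–21% under a 5% background quit rate, p of 0.40–0.50 and no dropout. The figures depend on the assumed rates. The absence of a minimum drop and of a control does not. A reader might go further and infer that the primary feasibility conclusion is compromised; it is not, since that endpoint does not use reduction. This is worth correcting before data are seen, but it is not a fundamental flaw.

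**What to change.** In sections 2.1.4, 10, 10.2 and 10.5, and in the synopsis where the goal is repeated:

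1. Count a participant as a reducer only if end-of-treatment consumption is at most half of baseline, quitters included. Use the same cigarette measure and recall window at both times, and confirm that the end-of-treatment questionnaire allows this.
2. Count participants with no end-of-treatment report as non-reducers, with 20 as the denominator.
3. Set the target percentage for this count before any data are seen. It need not stay at 50%.
4. Report any decrease descriptively only. State that neither count is by itself evidence of an app effect, because there is no control group and other cessation treatment is allowed.

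The cost is a few sentences, with no added visits or participants provided that the two cigarette questions already match. The downside is that the goal becomes harder to meet. Halving is a proposal; a smaller cut-off such as 25% is easier to reach but leaves a chance of up to about 11% under the assumptions shown.
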